8.1 Ventilation Strategy: Proportional Assist Ventilation (PAV+)

8.1.1 General Approach: PAV+

Patients randomized to the PAV+ group are treated with PAV+ on a PB840 or PB980 ventilator (Covidien LP, a Medtronic company). Only PAV+™ (Covidien LP, a Medtronic company) will be used. Proportional Pressure Support on the Draeger Evita 4 Ventilator may NOT be used. Patients will follow the PAV+ algorithm both day and night.

In the PAV+ strategy, the level of support (%Support or “gain”) will be adjusted to target a respiratory muscle pressure within normal range, without evidence of respiratory distress. At a minimum, patients will be assessed at least every 8 hours (or according to standard practice in each ICU if patient assessments are routinely performed more frequently than every 8 hours) to determine if adjustments need to be made to maintain respiratory muscle pressure (Pmus) within the target range. The Pmus target range is 5-10 cmH₂O, the clinical targets are a RR <35 and Vte > 5mL/kg PBW, while maintaining a pH in the range of 7.32-7.47. FiO₂ and PEEP are titrated clinically to maintain a SpO₂ 90-96%. Patients developing clinical instability or respiratory distress that cannot be alleviated on PAV+ will be changed to A/C mode and reassessed within 24 hours for criteria to resume PAV+.

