8.1.3 Adjusting PAV+

Adjustments are made to the ventilator settings immediately (5 minutes) after initiating PAV+ and at a minimum every 8 hours thereafter (or according to standard practice in each ICU if patient assessments are routinely performed more frequently than every 8 hours). If pH on arterial blood gas (ABG) is outside of the target range of 7.32-7.47, serial adjustments should be made immediately post ABG and ABG’s repeated every 30-60 minutes post ventilator adjustments until pH is back within the target range or patient meets criteria to switch to A/C.

The goal is to support patients’ breathing while maintaining an adequate amount of respiratory muscle activity to avoid atrophy of the diaphragm, or help to rehabilitate an already weakened diaphragm. The target range for respiratory muscle pressure (Pmus) is 5-10 cmH₂O, while maintaining a pH of 7.32-7.47. Some patients may be able to be supported within this target range comfortably, while others may not be able to generate a Pmus of 5 cmH₂O without developing clinical signs of respiratory distress. Therefore, adjustments are made to the ventilator settings according to whether Respiratory Distress is present or absent. FiO₂ and PEEP are titrated clinically to maintain a SpO₂ 90-96%. PEEP is set by the clinician according to clinical judgment at the bedside, but may be titrated taking into account clinically suspected intrinsic PEEP (PEEPi) and the ventilator automated

measurements of dynamic compliance (C_{PAV}) as described below. FiO_2 should be set and adjusted to the **lowest level required** to maintain SpO_2 90-96%. Patients developing prolonged apnea, respiratory distress or clinical instability will be changed to A/C mode and reassessed within 24 hours for criteria to resume PAV+.

The study protocol **defines Respiratory Distress as the presence of 2 or more** of the following signs:

Definition of Respiratory Distress

At least 2 of the following:

1. $SpO_2 < 90\%$
2. Sustained (>5 min) respiratory rate >35 b/min
3. Heart rate >140 b/min or a sustained (>5 min) increase of 20% from baseline
4. Systolic blood pressure >180 or <80 mmHg and/or systolic BP changes >30% from baseline
5. Increased anxiety
6. Use of accessory muscles
7. Complaint of dyspnea
8. Diaphoresis

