Immediately after initiating PAV+, and at least every 8 hours (minimum, see above) while on PAV+, determine if adjustments need to be made to the ventilator settings. Adjustments are made according to whether Respiratory Distress is present or absent.

Adjusting PAV+ if Respiratory Distress is present:

If Respiratory Distress is present, complete the following steps:

1. Assess PAV+ Resistance (R) and Compliance (C) measurements. If R_{TOT} is high (> 10 cmH₂O/L/s), treat any apparent cause of high resistance (eg. Secretions, bronchospasm). If C_{PAV} is low (<35 mL/cmH₂O), treat any apparent cause of decreased compliance (e.g., Pulmonary edema). Treat any cause of metabolic acidosis, if present.
2. Increase PEEP in steps of 2 cmH₂O until compliance no longer increases.
3. Increase FiO_2 as needed to keep SpO_2 90-96%
4. Increase PAV+ %Support in steps of 10% until respiratory distress resolves and $pH > 7.32$
5. Switch to A/C mode if one or more of the following occur during steps 1-4:
 - a. PAV+ %Support >85%
 - b. $FiO_2 > 60\%$ required to maintain $SpO_2 \geq 90\%$
 - c. **Clinical Instability**
 - d. Requiring neuromuscular blockade and/or sedation such that patient is no longer able to trigger the ventilator

Definition of Clinical Instability

Any 1 of the following:

1. Unstable hemodynamic status (SBP < 80 mmHg) with or without vasoactive drug
2. Vasopressor requirements >0.5 $\mu\text{g}/\text{kg}/\text{min}$ epinephrine/norepinephrine or equivalent
3. Active cardiac ischemia (dynamic ST changes on cardiac monitor or electrocardiogram)
4. Unstable arrhythmias (HR >140 or <50 with clinical signs of low cardiac output or SBP < 80 mmHg)
5. Uncontrolled hypertension (SBP > 180 mmHg)
6. Abrupt decrease in the level of consciousness (RASS -4 or -5 or SAS 1 or 2)
7. Dangerous agitation (RASS +4 or +3 or SAS 7)
8. Metabolic (or mixed) acidosis with $pH < 7.32$

9. Emergency situation that merits return to full ventilation (A/C) according to best clinical judgement

Patients requiring A/C ventilation should be reassessed within 24 hours for Criteria for Switching from A/C to PAV.

Adjusting PAV+ if Respiratory Distress is Absent:

If respiratory distress is absent, complete the following steps for adjusting %Support, PEEP and FiO₂:

1. Adjust the PEEP according to clinical judgment at the bedside. When determining best PEEP level for the patient, consider the following:

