 - a. Does increasing/decreasing the extrinsic (set) PEEP reduce the intrinsic PEEP (PEEPi)?
 - b. Does increasing/decreasing the extrinsic (set) PEEP improve compliance (C_{PAV})?
 - c. Choose the set PEEP which results in the lowest PEEPi and highest C_{PAV}
2. Adjust the FiO₂ to the lowest level required to maintain SpO₂ >90% (and in the range 90-96%).
3. Using the Pmus Calculator card, calculate the Pmus, peak as follows:
 - a. Observe the Peak airway pressure (Paw,peak) over 3-5 breaths and subtract the PEEP from the Paw, peak to obtain the Delta Paw (Delta Paw=Paw,peak – PEEP)
 - b. Line up the Delta Paw number with the white arrow by sliding the inner card of the Pmus calculator
 - c. The Pmus peak is the number displayed in the Pmus calculator window corresponding to the % Support set on the ventilator
4. Adjust the % Support according to the Pmus,peak as follows:
 - a. Pmus,peak <5 cmH₂O: Decrease gain in steps of 5-10% until Pmus,peak is in the target range of 5-10 cmH₂O; If Respiratory Distress develops while decreasing the gain, follow the algorithm for Respiratory Distress
 - b. Pmus, peak >10 cmH₂O: Increase the gain in steps of 5-10% until Pmus,peak is in the target range of 5-10 cmH₂O; If Respiratory Distress develops while increasing the gain, follow the algorithm for “Respiratory Distress”
 - c. Pmus, peak 5-10 cmH₂O: Target range achieved: no adjustments required unless:
 - i. RR <12 or >35 or Vte<5 or >10 mL/kg PBW, obtain arterial blood gas (ABG):
 1. If ABG demonstrates a respiratory alkalemia, treat any apparent cause of hyperventilation, (eg. pain, anxiety, metabolic acidosis), then decrease gain in steps of 5-10% until Vte <8 mL/kg PBW OR pH<7.47
 2. If ABG demonstrates a respiratory acidemia OR respiratory distress develops:
 - a. Increase PEEP in steps of 2 cmH₂O until compliance no longer increases.
 - b. Increase FiO₂ as needed to keep SpO₂>90%
 - c. Increase PAV %Support in steps of 10% until pH>7.32 and respiratory distress resolves
 - d. Switch to A/C mode if one or more of the following occur during steps a-c:
 - i. PAV %Support >85%
 - ii. FiO₂ >60% required to maintain SpO₂ ≥90%
 - iii. **Clinical Instability** (see definition)
 - iv. Requiring neuromuscular blockade and/or sedation such that patient is no longer able to trigger the ventilator

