8.2 Ventilation Strategy: Pressure Support Ventilation (PSV)

8.2.1 General Approach: PSV

Patients randomized to the PSV group are treated with PSV on any ventilator capable of delivering standard pressure support mode. The make and model of the ventilator used to deliver PSV will be recorded as part of the data set. Patients will follow the PSV algorithm both day and night.

In the PSV strategy, the level of pressure support will be adjusted according to routine clinical parameters, targeting a comfortable respiratory rate and tidal volume. At a minimum, patients will be assessed at least every 8 hours (or according to standard practice in each ICU if patient assessments are routinely performed more frequently than every 8 hours) to determine if adjustments need to be made to maintain patient comfort, and ensure adequate ventilation and oxygenation. The clinical targets are a RR 12-35 and V_{te} 5-10 mL/kg PBW, while maintaining a pH in the range of 7.32-7.47. FiO_2 and PEEP are titrated clinically to maintain a SpO_2 90-96%. PEEP is set by the clinician according to clinical judgment at the bedside. FiO_2 should be set and adjusted to the **lowest level** required to maintain SpO_2 90-96%. Patients developing respiratory distress or clinical instability will be changed to A/C mode and reassessed within 24 hours for criteria to resume PSV.

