1. Unstable hemodynamic status (SBP < 80 mmHg) with or without vasoactive drug
2. Vasopressor requirements > 0.5 $\mu\text{g}/\text{kg}/\text{min}$ epinephrine/norepinephrine or equivalent
3. Active cardiac ischemia (dynamic ST changes on cardiac monitor or electrocardiogram)
4. Unstable arrhythmias (HR > 140 or < 50) with clinical signs of low cardiac output or SBP < 80 mmHg)
5. Uncontrolled hypertension (SBP > 180 mmHg)
6. Abrupt decrease in the level of consciousness (RASS -4 or -5 or SAS 1 or 2)
7. Dangerous agitation (RASS +4 or +3 or SAS 7)
8. Metabolic (or mixed) acidosis with pH < 7.32
9. Emergency situation that merits return to full ventilation (A/C) according to best clinical judgement

Patients requiring A/C ventilation should be reassessed within 24 hours for **Criteria for Switching from A/C to PSV**.

Adjusting PSV if Respiratory Distress is Absent:

If respiratory distress is absent, adjust the level of pressure support, PEEP and FiO_2 as follows:

1. Adjust the PEEP according to clinical judgment at the bedside
2. Adjust the FiO_2 to the lowest level required to maintain $\text{SpO}_2 > 90\%$ and in the range 90-96%.
3. If patient appears comfortable (RR 12-35 and Vt 5-10 mL/kg PBW): target range achieved.
No adjustments required unless one of the following occurs:
 - a. If RR < 12 or > 35 or Vte < 5 or > 10 mL/kg PBW, obtain arterial blood gas (ABG):
 - i. If ABG demonstrates respiratory alkalemia, treat any apparent cause of hyperventilation (eg. pain, anxiety, metabolic acidosis), then decrease PS in steps of 2-3 cmH₂O until pH < 7.47 OR Vte < 8 mL/kg PBW
 - ii. If ABG demonstrates respiratory acidemia OR respiratory distress develops:
 1. Increase PS in steps of 2-3 cmH₂O until pH > 7.32 and respiratory distress resolves
 2. Switch to A/C mode if one or more of the following occur during above steps:
 - a. PS > 20 cmH₂O
 - b. PS + PEEP > 30 cmH₂O
 - c. $\text{FiO}_2 > 60\%$ required to maintain $\text{SpO}_2 \geq 90\%$
 - d. Clinical Instability**
 - e. Requiring neuromuscular blockade and/or sedation such that the patient is no longer able to trigger the ventilator

Patients requiring A/C ventilation should be reassessed within 24 hours for **Criteria for Switching from A/C to PSV**.

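### Protocol 8.1.3, step 4a: PAV+ gain is lowered at low effort without the slow-rate gas check used elsewhere, and in respiratory acidosis the step conflicts with the section's own pH rule

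*Protocol*

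**What the plan says.** **PAV+ arm, no distress (Protocol 8.1.3).** The action depends on Pmus,peak.

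- Step 4a, Pmus below 5 cmH₂O: "Decrease gain in steps of 5-10% until Pmus,peak is in the target range of 5-10 cmH₂O". The only exit written into the step is the onset of Respiratory Distress. That needs two of eight signs, and neither a low rate nor a low pH is among them.
- Step 4c, Pmus 5–10: leave the settings alone unless the trigger is met, "RR <12 or >35 or Vte<5 or >10 mL/kg PBW, obtain arterial blood gas (ABG"). Gain is lowered if the gas shows respiratory alkalemia. If it shows respiratory acidemia, support is raised, with a switch to A/C if limits are reached.

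**PSV arm, no distress (8.2.3, step 3a).** The same trigger applies: "If RR < 12 or > 35 or Vte < 5 or > 10 mL/kg PBW, obtain arterial blood gas (ABG").

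**General targets.** For PAV+ (8.1.1), "the clinical targets are a RR <35 and Vte > 5mL/kg PBW, while maintaining a pH in the range of 7.32-7.47", with no lower rate limit. For PSV (8.2.1) there is one: "The clinical targets are a RR 12-35 and V_{te} 5-10 mL/kg PBW".

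**Section-level rules in 8.1.3.** If a gas is outside pH 7.32–7.47, "serial adjustments should be made immediately post ABG", with repeat gases every 30–60 minutes until pH is back in range or the patient qualifies for A/C. Also, "Patients developing prolonged apnea, respiratory distress or clinical instability will be changed to A/C mode". Clinical Instability includes "Abrupt decrease in the level of consciousness (RASS -4 or -5 or SAS 1 or 2"), metabolic or mixed acidosis below pH 7.32 (item 8), and an emergency judged to need full ventilation (item 9).

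**The concern.** Low effort together with a slow rate is a picture of over-sedation, and 8.1.2 itself warns that over-sedation on PAV+ can lead to respiratory acidosis. Low effort can equally mean too much assistance, and then lowering gain is right. A gas separates the two. Read literally, step 4a asks for no gas, so the patient making less effort gets a weaker check than the patient at Pmus 5–10 or the comparable PSV patient.

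At stake is patient safety in the PAV+ arm: a period of reduced support in someone who is hypoventilating. The primary outcome, the other endpoints and the analysis are not involved.

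**Working it through.** The plan gives no figure to reproduce. The check is a trace of the text, followed by an illustration.

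**1. Same patient, three places.** No distress, RR <12, Vte 5–10 mL/kg PBW:

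| Setting | Text | Gas required because of the rate? | What lowers support |
|---|---|---|---|
| PAV+, Pmus 5–10 | 8.1.3, step 4c.i | Yes | A gas showing alkalemia |
| PSV | 8.2.3, step 3a | Yes | A gas showing alkalemia |
| PAV+, Pmus <5 | 8.1.3, step 4a | No | Pmus alone |

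**2. pH <7.32, pure respiratory acidosis, Pmus <5, no distress.**

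- Step 4a: decrease gain.
- Section-level pH rule: keep adjusting until pH is in range. No direction is named, but lowering support would not get there.
- Clinical Instability item 8: not met, because it covers metabolic or mixed acidosis only.
- Steps that raise support and then switch to A/C: written only under 4c.

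The step and its governing paragraph therefore point in opposite directions.

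**3. Other rules that could fill the gap.**

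- 8.3.3 requires a gas after the Pressure Support Trial, at 30–60 minutes after initiation, and when minute ventilation (VE) changes significantly. It gives Vte <5 or >10 mL/kg as an example trigger and does not name the rate.
- 8.1.2 uses baseline Vt and VE to watch for acidosis and sets a low-VE alarm at 5 L/min. Its alarm list has no low-rate limit, and the low-Vte alarm is 0 mL.
- 8.4.1 advises reducing sedation when RASS or SAS is below target.
- The consciousness item in Clinical Instability needs an abrupt fall, so steady moderate sedation is outside it. Item 9 leaves A/C open to judgement.

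These narrow the exposure. None supplies the rate trigger or reverses 4a at step level.

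**4. Illustration.** Assumed inputs: man of 175 cm, RR fixed at 11, Vte 7 mL/kg, Pmus 3 cmH₂O, 10-point steps. Gain 70% is the 8.1.2 starting value. Vte is assumed proportional to total inflating pressure T.

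- PBW = 50 + 0.91 × (175 − 152.4) = 70.6 kg
- T = Pmus / (1 − gain) = 3 / 0.30 = 10.0 cmH₂O
- Vte = 7 × T / 10 mL/kg
- VE = RR × Vte × PBW = 11 × 7 × 70.57 = 5.43 L/min at the start

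*No compensation* (Pmus stays 3):

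- 60%: T = 3/0.40 = 7.5, Vte 5.25, VE 4.08
- 50%: T = 3/0.50 = 6.0, Vte 4.20, VE 3.26; the 8.3.3 Vte trigger is met at step 2

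*Half compensation* (Pmus rises by half of what would hold T at 10):

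| Gain | Pmus | T | Vte (mL/kg) | VE (L/min) |
|---|---|---|---|---|
| 60% | 3.5 | 8.75 | 6.13 | 4.75 |
| 50% | 4.0 | 8.00 | 5.60 | 4.35 |
| 40% | 4.5 | 7.50 | 5.25 | 4.08 |
| 30% | 5.0 | 7.14 | 5.00 | 3.88 |

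VE falls by (5.43 − 3.88)/5.43 = 28.6%. Vte never drops below 5, so the Vte trigger is not met before Pmus reaches 5 and 4c takes over. The VE alarm does sound after step 1 (4.75 <5).

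*Full compensation:* T stays at 10 and VE does not fall; Pmus is 5 at 50% gain.

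**5. How far the alarm helps.** It is fixed, not scaled to body size. VE equals 5 L/min at PBW = 5000 / (11 × Vte):

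- Before any step (Vte 7): 64.9 kg; smaller patients are already alarming
- After step 1, half compensation (Vte 6.125): 74.2 kg, a man of about 179 cm
- After step 1, no compensation (Vte 5.25): 86.6 kg, a man of about 193 cm

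Above the last two weights, the alarm is silent after step 1 in the respective scenario.

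**The case against.** **Appendix C.** Section 8.0 places the ventilator algorithms in Appendices C and D. In the extracted Appendix C, the gas box follows the three Pmus columns and does not sit inside the 5–10 cell. If it spans all columns, the bedside card already closes the gap. The 5–10 cell ends by leading into an exception, so the layout could mean either. This stands as a real limit: the point is about the prose of 8.1.3.

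**The pH rule already gives the direction.** The Pmus target is tied to pH 7.32–7.47, and adjustments continue until pH is in range, so a sensible reader would not lower support in respiratory acidosis. This largely stands. What remains is a conflict between a step and its paragraph, and the rule acts only once a gas exists.

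**Existing safeguards are substantial.** They are. A 29% fall from a recorded baseline VE could reasonably count as a significant change under 8.3.3. That rule sets no threshold, however, and does not catch a patient whose rate was slow at baseline.

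**The PSV trigger is also nested**, under the line describing a comfortable patient. True, but that is the only ventilation branch in the PSV no-distress algorithm, and the trigger acts when the patient leaves that range. PAV+ has three branches with the trigger under one.

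**The worked case is chosen.** It is. Gain 70% is the starting setting; enrolment requires pH of at least 7.32, resumption from A/C requires pH above 7.32, and a gas follows the Pressure Support Trial. The case therefore fits later checks better than the first adjustment at 5 minutes.

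**Step 4a serves a purpose.** Low effort at high gain often means over-assistance, and 8.1.3 aims to avoid diaphragm atrophy. Section 4.4.3 reports that the gain algorithm was piloted (n=52) with safety shown. Both argue for keeping 4a, with a check added.

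**Conclusion.** The point holds for the prose of 8.1.3 and is minor. Step 4a lacks the rate-triggered gas that 4c.i and the PSV algorithm have, and in pure respiratory acidosis it conflicts with the section's pH rule. Exposure is limited to PAV+ patients with Pmus <5 and no distress, mainly at checks after the first.

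Three stronger readings are tempting, and the documents do not support them:

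- *That no gas is taken before gain is lowered.* Section 8.3.3 requires one after the Pressure Support Trial and another 30–60 minutes after initiation.
- *That the protocol as a whole directs support downwards in acidosis.* The pH rule in 8.1.3 implies the opposite; only the step says so.
- *That trial results could be distorted.* Nothing here touches an endpoint or an analysis.

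The calculated fall in ventilation, from none to 29% with Vte staying at or above 5 mL/kg, depends on assumed compensation, a fixed rate and a chosen patient. The textual finding does not. How often such patients occur, and what their pH would be, cannot be derived from the documents. The point would lapse on the bedside card if Appendix C already routes the gas box to all Pmus columns.

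**What to change.** Add to step 4a only: *If RR <12 or Vte <5 mL/kg PBW, obtain an ABG before decreasing gain. Do not decrease gain while pH is <7.32 from respiratory acidosis; lighten sedation and follow 4c.i.2, including the switch to A/C.*

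Leave 4b and 4c unchanged. Check the Appendix C card and align it only if its routing differs. The wording reuses the protocol's own gas trigger, pH limit and acidemia steps.

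The cost is two sentences and possibly one card edit, a few extra gases in PAV+ patients with low effort and a low rate or volume, and a short delay in lowering gain while the gas is run.

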8.1.4 Resuming PAV+ after A/C ventilation

Patients switched to A/C ventilation as per study protocol should be reassessed within 24 hours, and at least once daily thereafter, for **Criteria for Switching from A/C to PAV+**. **These are the minimum criteria for switching from A/C back to PAV+**. If all of the criteria for switching from A/C to PAV are present, the patient **must** be tried on

PAV+: follow the Initiation of PAV+ protocol, with initial and subsequent adjustments made to PAV+ settings according to the Algorithm for Adjusting PAV+. After a trial of PAV+, patients may be switched back to A/C mode if they meet criteria according to the PAV+ ventilation strategy algorithm. The **Criteria for Switching from A/C to PAV+** are as follows:

Criteria for Switching from A/C to PAV+:

1. Able to trigger ventilator breaths
2. On assist/control with the following settings:
 - a. AC/VC: $P_{plat} \leq 30 \text{ cmH}_2\text{O}$ with V_t 6-8 ml/kg OR
 - b. AC/PC: $PC + PEEP \leq 30 \text{ cmH}_2\text{O}$
3. $PaO_2 \geq 60 \text{ mmHg}$ or $SpO_2 \geq 90\%$ on $FiO_2 \leq 0.60$ and $PEEP \leq 15 \text{ cm H}_2\text{O}$
4. Metabolic disorders corrected; $pH > 7.32$
5. Stable hemodynamic status: stable or decreasing doses of vasopressors for ≥ 6 hours
6. Absence of **Clinical Instability** (see definition, above)

8.2 Ventilation Strategy: Pressure Support Ventilation (PSV)

8.2.1 General Approach: PSV

Patients randomized to the PSV group are treated with PSV on any ventilator capable of delivering standard pressure support mode. The make and model of the ventilator used to deliver PSV will be recorded as part of the data set. Patients will follow the PSV algorithm both day and night.

In the PSV strategy, the level of pressure support will be adjusted according to routine clinical parameters, targeting a comfortable respiratory rate and tidal volume. At a minimum, patients will be assessed at least every 8 hours (or according to standard practice in each ICU if patient assessments are routinely performed more frequently than every 8 hours) to determine if adjustments need to be made to maintain patient comfort, and ensure adequate ventilation and oxygenation. The clinical targets are a RR 12-35 and V_{te} 5-10 mL/kg PBW, while maintaining a pH in the range of 7.32-7.47. FiO_2 and PEEP are titrated clinically to maintain a SpO_2 90-96%. PEEP is set by the clinician according to clinical judgment at the bedside. FiO_2 should be set and adjusted to the **lowest level** required to maintain SpO_2 90-96%. Patients developing respiratory distress or clinical instability will be changed to A/C mode and reassessed within 24 hours for criteria to resume PSV.

